NCT Study Title: Inflammation and Daily Life Study

Grant Study Title: Can an anti-inflammatory medication reduce loneliness?

NCT: NCT03771612

Original Document Date: January 7, 2022

Modified with Requested Updates: December 20, 2024

Study Protocol

Due to the relationships between loneliness and a variety of poor health outcomes and mortality, loneliness is increasingly being recognized as an important public health issue. Despite the relevance of loneliness for health, including evidence suggesting the effects may be particularly pronounced for middle-aged adults, loneliness is a highly understudied topic in mid-life in need of further research. One potential mechanism for the effect of loneliness on health is inflammation. Lonely individuals have heightened inflammation, and inflammation can increase feelings of loneliness. Furthermore, loneliness and inflammation share similar psychological states, both marked by hypersensitivity to the social world, including increased sensitivity to both negative and positive social cues (i.e., social threat and social reward). Thus, by breaking the cycle between inflammation and loneliness, and altering the underlying hypersensitive psychological state, it is possible that an anti-inflammatory drug may lead to improvements in loneliness. However, to our knowledge, no studies have explicitly tested this. The objective of this study is to address this gap in the literature and test the effect of an anti-inflammatory medication on loneliness in a sample of middle-aged adults and to examine the social psychological mechanisms that may underlie any benefits.

This randomized double-blind placebo-controlled study will test the effect of an NSAID (naproxen) on loneliness and explore which psychological mechanisms are best targeted by an NSAID. Participants, all middle-aged adults screened for high levels of loneliness, will be randomized into a 2-week naproxen or placebo intervention. All participants will complete pre- and post-intervention sessions online to assess self-report psychological outcomes, inflammatory activity, and performance on behavioral tasks.

Participants will be men and women, ages 45-59, who all have high levels of loneliness. High loneliness scores will be assessed using the UCLA Loneliness Scale, with eligible subjects having a score of 41 or greater (approximately 20-25% of middle-aged adults), which has been previously used by our group to define a high loneliness group.

Participants will be recruited from the greater Los Angeles community using advertisements. All interested participants will first complete a structured telephone interview in order to assess eligibility; prospective participants with co-morbid medical conditions or characteristics known to affect inflammation or put them at undue risk will be ineligible to participate. Notably, participants with current Major Depressive Disorder will be excluded. However, we will control for depressive symptoms in analyses examining effects on loneliness to test whether the effect of NSAIDs on loneliness hold over and above effects on depression.

At baseline, participants will complete their first session online with an experimenter. Here, they will provide blood spots, complete self-report measures as well as several psychological tasks. Psychological tasks will include a task in which participants view negative social images and make ratings of their affective responses. Participants will also include a social/monetary reward task (revised Monetary Incentive Delay Task; Knutson et al., 1999) in which they will press a button once a target flashes on the screen in order to win money or see a close other or smiling stranger. Reaction times will be assessed, with faster reaction times indicating greater reward anticipation. We are

particularly interested in the difference in reaction times to close others vs. control targets.

They will be mailed their pill packs for the intervention. Following the baseline assessment, participants will take one 200 mg pill immediately after waking up each day, and another 200 mg pill an hour before going to sleep, daily for 2 weeks. By random assignment, half of the participants will take naproxen and half will take the same dose of placebo. The random allocation sequence will be generated by a statistical consultant who was not involved in running participants and will be kept by the UCLA Pharmacy to ensure proper drug preparation for each participant. Randomization will be done using a computerized uniform random number generator; males and females will be randomized separately in permuted blocks of 4.

Naproxen was chosen as it is available as a generic (and thus low-cost) drug, has a less frequent dosing schedule (i.e., twice daily) than some other NSAIDs (e.g., ibuprofen, taken every 4-6 hours), and has been associated with lower risk for adverse cardiovascular side effects compared to other NSAIDs. Furthermore, naproxen can reduce depressive symptoms in both animals and humans, providing evidence that it can affect psychological states. Additionally, the effect of NSAIDs on circulating levels of inflammation are inconsistent, but there is some meta-analytic evidence to suggest that naproxen specifically may lead to significant decreases in C-reactive protein, suggesting naproxen may be one of the best NSAIDs for reducing circulating levels of inflammation. The dosing of 400 mg/daily was chosen based on maximum over-the-counter recommendations.

Over the 2-week period, subjects will complete daily and weekly (online) measures of loneliness, other social psychological outcomes, and any side effects. Additionally, participants will receive text message reminders to take their pills, and report on symptoms, adherence, and any side effects (monitored by study staff). Participants will be asked to report on a full range of symptoms (mild, moderate, severe) in both a checklist and an open-ended fashion. Adverse events will be reported to the study physician, who will not be blinded to condition. If, at any point in the study, participants report mild side effects (e.g., diarrhea, heartburn for 2 consecutive days or more), their dose will be reduced by half to 200 mg each day. If participants report moderate to severe side effects (e.g., stomach pain, shortness of breath or trouble breathing), they will be removed from the study. At the end of the 2-week intervention, participants will get online again with an experimenter to provide another blood sample (to be mailed back) as well as to complete self-report measures and behavioral tasks, similar to the baseline assessment. In addition, participants will be contacted again 2 weeks later to assess measures of loneliness.

IRB amendment (5/2021):

Major changes to study protocol for COVID and financial reasons

Minor Amendment - Types of change(s) proposed.

Check all that apply:

- Clarification or technical change
- **Minor increase/decrease in number of Study participants**
- Narrowing of the inclusion criteria

- Broadening of the exclusion criteria
- **Changes in the dosage or form (e.g., tablet to liquid) but not the route of administration of an approved drug**
- **Increase or decrease in the number of safety monitoring visits provided that there is no impact on subject safety.**
- Addition or deletion of study sites
- **Change in payments to study participants**
- **Minor changes to recruitment materials**
- **Minor changes to screening procedures**
- **Change in funding (for example, addition of new funding or completion of grant) – Please describe below AND update the funding status in section 6.2 in the main application**
- **Other**

Major Amendment - Types of change(s) proposed.

Check all that apply:

- **Change in study design of a protocol approved by the full board of the IRB**
- Change in status of study participants (e.g., study participant becomes prisoner, ward, or pregnant in a protocol not approved for these populations (Note: This primarily applies to medical or treatment studies.)
- Addition of a procedure not approvable using expedited review procedures (e.g., ionizing radiation)
- Changes that increase risk or discomfort to study participants
- **Substantive changes to a consent form or other study documents distributed to subjects.**
- **Other**

Numerous reasons have converged and required us to change this study protocol drastically. First, because of the COVID-19 pandemic, we want to minimize all in-person contact as much as possible for participants and staff. Second, the budget/finances available to run this study have been drastically reduced because the pandemic as well. As such we are proposing the following changes to the study:

- Instead of n=100, we will have a final sample of n=50 (necessary for cost-saving)
- As the inflammatory markers were only an exploratory aim of the study, we will be eliminating all inflammatory markers / blood draws from the study for cost-saving reasons, as well as to be able to allow participants to complete the study entirely from their own homes for COVID safety reasons. All references to blood draws, inflammatory markers, gene expression analyses, medical records, medical tests, UCLA health phlebotomy, etc. have been removed from all materials/throughout the IRB.
- As such, all study procedures (consent, all questionnaires, tasks, drugs will be mailed to participants' homes, etc.) will take place from the participant's own homes. Participants will complete all questionnaires on their own online via Qualtrics. Tasks that would have been done at UCLA with study staff will now be done in a virtual session with study staff. All relevant sections/materials of the IRB have been updated to reflect this.

- Instead of participants taking naproxen/placebo twice daily for 4 weeks, they will take it twice daily for 2 weeks, for both cost-saving and safety reasons.
- As the over the counter indication for naproxen/Aleve is 10 days, and we are proposing 14 days, this will also eliminate the need to have any safety blood panels completed prior to starting the study. As noted above, all blood draws previously done for scientific reasons have been eliminated from this study. As such, the safety blood draws are not feasible for this study, for cost reasons. If the IRB would be more amenable to 10 days for safety reasons to drop these blood draws, we are willing to go down to 10 days as well.
- Relatedly, we have re-classified this study as minimal risk. We have greatly reduced the risks associated with this study by cutting down the time of the drug in half from 4 weeks to 2 weeks. We are also removing all blood draws associated with the study. We believe it is fair to classify this study as minimal risk now.
- As the study is considerably safer for participants, with this reduced dosage, and that all study procedures will be taking place online, we have changed the consent form to be done online by study staff, not just the study physician. Participants will be emailed a copy of the consent form to review at their convenience. They will be encouraged to ask the study staff any questions they have, including the study physician, in advance of signing the consent form. Prior to the participant's signing of the consent form, a member of the study team will contact the participant and go over and confirm that the participant has understood the form and has no remaining questions. Once they are comfortable, participants will sign the consent form virtually by completing a Qualtrics form. All relevant sections of the IRB have been updated to reflect this change.
- We have shortened the 2-week follow-up online questionnaires to a shorter session (30 minutes) and dropped the 4-week survey altogether, for cost-saving reasons
- All participant payments and time required has also been updated to reflect the shortened study design

IRB amendment (7/2021):

Study amended to include blood spot collection for inflammatory assessment. Blood spot collection devices will be mailed to participants and sent back to us for analysis.

Statistical Analysis Plan

Primary:

To examine whether naproxen reduces feelings of loneliness, we will use repeated measures analyses to examine time (pre- vs. post-intervention) by condition (naproxen vs. placebo) interactions on loneliness.

To examine whether naproxen reduces sensitivity to social threat, we will use repeated measures analyses to examine time (pre- vs. post-intervention) by condition (naproxen vs. placebo) interactions on self-reported ratings to negative social images. We anticipate that subjects in the naproxen (vs. control) condition will rate negative images as less negative from pre-to-post intervention.

To examine whether naproxen reduces sensitivity to social reward, we will use repeated measures analyses to examine time (pre- vs. post-intervention) by condition (naproxen vs. placebo) interactions on reaction times to social reward (with faster reaction times indicative of greater reward). Specifically, we expect that subjects in the naproxen (vs. placebo) condition will show less of a difference in reaction times to viewing close others vs. control targets from pre- to post-intervention.

Secondary:

To examine whether naproxen reduces inflammatory gene expression, we will use repeated measures to examine time (pre- vs. post-intervention) by condition (naproxen vs. placebo) interactions on the inflammatory gene composite measure.

To examine whether naproxen reduces feelings of loneliness at follow-up (2 weeks post-intervention), we will use repeated measures analyses to examine time (pre- vs. post- vs. follow-up intervention) by condition (naproxen vs. placebo) interactions on loneliness.

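### Participants with moderate to severe side effects leave the study, not just the drug, so their outcomes are apparently lost

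*Combined protocol and SAP*

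**What the plan says.** The Study Protocol sets two tiers of response to side effects. For mild ones, "their dose will be reduced by half to 200 mg each day", and the participant carries on. For the more serious tier: "If participants report moderate to severe side effects (e.g., stomach pain, shortness of breath or trouble breathing), they will be removed from the study". Nothing provides for stopping the pills while continuing assessment, and neither IRB amendment (5/2021 or 7/2021) changes the rule. The same section adds: "Adverse events will be reported to the study physician, who will not be blinded to condition".

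The post-intervention session comes at the end of the two weeks, and loneliness is measured again two weeks after that. The nearest contrary text is in the design overview of the Study Protocol: "All participants will complete pre- and post-intervention sessions online". It is a general description and does not mention people who have been removed.

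All three primary tests in the SAP are time-by-condition interactions from before to after the intervention. Of the two secondary tests, one does the same for inflammatory gene expression and the other adds the follow-up loneliness score. The SAP gives no analysis population and no rule for missing outcomes. The 5/2021 amendment sets the size: "we will have a final sample of n=50".

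**The concern.** Removal depends on symptoms, such as stomach pain, that arise after randomisation and that an NSAID may produce. If removal ends data collection, the groups compared are those who tolerated their assigned pill, not those randomised. When removals differ between arms in number or in kind, and those removed would have changed differently from those who stayed, the comparison is biased.

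The direction cannot be known in advance. With more removals on naproxen, the bias favours naproxen if those removed would have done worse, and placebo if they would have done better. All five SAP tests are exposed, and the SAP contains nothing that would offset the loss.

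**Working it through.** **Reading the text.** Two adjacent rules use different actions: one acts on the dose, the other on study participation. The specific removal rule outweighs the overview sentence, which is silent on removed participants. That outcomes stop being collected is still an inference, though the natural one.

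**Inputs.** The documents give the total of 50 and equal allocation, hence about 25 per arm. They give no power calculation, dropout rate or removal rate, so there is no figure of the plan's own to reproduce. Assumed: two-sided alpha 0.05; removals of 3 versus 1 or 5 versus 1 (naproxen versus placebo); a gap d of 0.5 to 0.8 SD in mean pre-to-post change between those removed and those retained, the same in both arms.

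**Bias if those removed are left out.** With a proportion p removed, the retained mean minus the all-randomised mean is −p × d in each arm, so

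bias = |p1 × d1 − p0 × d0|.

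The standard error (SE) is √(1/n1 + 1/n0) in SD units, and type I error comes from the noncentral t distribution.

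| Removed | Gap | Bias (SD) | SE | Bias/SE | Type I error |
|---|---|---|---|---|---|
| 3 vs 1 | 0.5 | (0.12 − 0.04) × 0.5 = 0.04 | 0.295 (22 vs 24) | 0.14 | 5.2% |
| 3 vs 1 | 0.8 | 0.08 × 0.8 = 0.064 | 0.295 | 0.22 | 5.5% |
| 5 vs 1 | 0.5 | (0.20 − 0.04) × 0.5 = 0.08 | 0.303 (20 vs 24) | 0.26 | 5.8% |
| 5 vs 1 | 0.8 | 0.16 × 0.8 = 0.128 | 0.303 | 0.42 | 7.0% |

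Equal removals with equal gaps give zero. Simulation gave matching type I errors, and the bias changes sign when d does.

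**Does a mixed model alone cure it?** With baseline kept, the post score missing and a gap not visible at baseline, simulated maximum-likelihood fits gave a bias of 0.040 SD (3 vs 1, d = 0.5) and 0.128 SD (5 vs 1, d = 0.8), the same as leaving those people out.

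**Bias left if stoppers are invited but only some attend.** If a of r stoppers attend and are typical of stoppers, bias per arm = d × (r/25 − a/(25 − r + a)). If the one placebo stopper attends, that arm contributes zero.

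- 2 of 3 on naproxen attend: d × (0.12 − 2/24) = 0.018 to 0.029 SD.
- 3 of 5 attend: d × (0.20 − 3/23) = 0.035 to 0.056 SD.
- All attend: zero.

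**Power.** With 25 per arm, the effect detectable with 80% power is 0.809 SD (t test). Take that as the true on-drug effect. If stoppers are kept, a fraction p of the naproxen arm stops and retains a share k of the benefit, so the effect becomes 0.809 × (1 − p(1 − k)).

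| | 3 of 25 stop | 5 of 25 stop |
|---|---|---|
| Left out, no selection | 76% | 74% |
| Kept, no benefit retained | 0.809 × 0.88 = 0.712 SD, 69% | 0.809 × 0.80 = 0.647 SD, 61% |
| Kept, half retained | 75% | 71% |
| Kept, all retained | 80% | 80% |
| Share retained for equal power | 64% | 66% |

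**The case against.** - **The data loss is inferred.** The text never says that assessment stops, and the overview sentence can be read the other way. This stands as a caveat. If the sponsor does intend to keep assessing these people, the rewording only makes that explicit.
- **The effect is small.** The bias is well below the standard error. No document supports 5 versus 1 removals, and over-the-counter dosing, screening and dose-halving should keep removals few. This stands, and it limits how strongly the point can be put.
- **Daily and weekly loneliness scores are already planned.** Suppose a mid-treatment score correlates 0.5 to 0.7 with the post change and already shows half to all of the gap. The 0.128 SD bias would then fall to roughly 0.128 × (1 − 0.7 × 1) = 0.04 up to 0.128 × (1 − 0.5 × 0.5) = 0.10 SD. But the SAP tests do not use these scores, early stoppers may have few of them, and they do nothing for the two task outcomes.
- **The fix dilutes the effect.** If stoppers keep no benefit, the dilution is 0.809 × 0.12 = 0.10 SD or 0.809 × 0.20 = 0.16 SD, more than the bias removed in the matching case. This is the strongest objection, and the power loss is real. However, the higher power from leaving stoppers out assumes no selection, which cannot be checked without their scores. A supportive on-drug analysis keeps that question open.
- **An unblinded physician would decide on task sessions.** Attendance could then differ by arm on two of the three primary outcomes. Recording the reason documents this but does not prevent it. It still loses less data than removing everyone.
- **The 50 may mean completers.** The figures here assume 50 randomised. If removed people are replaced, power is restored but the randomised comparison is not.

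**Conclusion.** The concern holds. The plan removes people from the study after randomisation for a reason the drug may cause, and neither the protocol nor the SAP keeps their outcomes or says how to handle the gap. The probable size is small: 0.04 to 0.064 SD of bias at 3 versus 1 removals and 0.08 to 0.128 SD at 5 versus 1. Type I error reaches 7.0% only if both the larger imbalance and the 0.8 SD gap occur. The direction is unknown. These figures rest on assumed removal rates and gaps, on 25 randomised per arm, and on reading removal as the end of assessment. It is a change that should be made, not a fatal flaw.

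**What to change.** **Protocol.** Replace the removal clause with: *they will stop study drug and, unless they withdraw consent, will still be invited to the online post-intervention questionnaires, to the virtual task session and blood spot (where they are willing and the study physician agrees on safety grounds, with the reason recorded), and to the 2-week follow-up.* The thresholds for halving or stopping the pills stay as they are. The reason is recorded because the physician knows the allocation.

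**SAP.** Add: *all randomised participants are analysed in their assigned arm with a likelihood-based mixed model for repeated measures using all available scores; numbers stopping study drug and numbers with missing outcomes are reported by arm; an analysis limited to those who stayed on study drug is supportive.* That supportive analysis remains open to the selection described above.

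**Cost.** One protocol sentence, one SAP sentence and an IRB amendment. At 3 versus 1 or 5 versus 1 removals, this means 4 or 6 extra sets of questionnaires, virtual task sessions, blood-spot kits and 30-minute follow-ups, with their payments. The remote design described in the 5/2021 amendment makes this practical: "Participants will complete all questionnaires on their own online via Qualtrics", and "Tasks that would have been done at UCLA with study staff will now be done in a virtual session with study staff". The statistical price is that the main estimate includes off-drug time, and power falls if stoppers keep less than about two thirds of the benefit.

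### The primary loneliness test compares change scores and omits baseline loneliness; it is valid, but ANCOVA would usually be more precise at almost no cost

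*Combined protocol and SAP*

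**What the plan says.** The Statistical Analysis Plan, under Primary, states for loneliness: "we will use repeated measures analyses to examine time (pre- vs. post-intervention) by condition (naproxen vs. placebo) interactions on loneliness". It names no baseline-loneliness covariate, no sex term and no constraint on the baseline means. The other two primary outcomes, ratings of negative social images and reaction times to social reward, use the same time-by-condition form.

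The Study Protocol supplies the rest of the setting:

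- The baseline value is already planned: "All participants will complete pre- and post-intervention sessions online to assess self-report psychological outcomes".
- Eligibility is settled in a separate, earlier step: "All interested participants will first complete a structured telephone interview in order to assess eligibility". The entry rule has "eligible subjects having a score of 41 or greater (approximately 20-25% of middle-aged adults".
- Half the participants go to each arm, and "males and females will be randomized separately in permuted blocks of 4". Baseline loneliness is not a stratification factor.
- The only covariate named for loneliness is depression: "we will control for depressive symptoms in analyses examining effects on loneliness". Its timing is not stated, and the SAP section does not repeat it.

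The IRB amendment of 5/2021 cut the sample from 100 for cost reasons: "we will have a final sample of n=50".

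**The concern.** A change score subtracts the whole baseline value, which amounts to fixing the regression slope of post on pre at 1. If the true slope is lower, the subtraction adds noise. ANCOVA estimates the slope and removes that noise. Because randomisation does not balance baseline loneliness beyond chance, the adjustment also deals with chance imbalance efficiently.

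What is at stake is precision, not validity. With 50 people and no budget for more, a plan that leaves recoverable precision unused lowers the chance of detecting a real effect and widens the interval if there is none.

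**Working it through.** **Inputs.** From the documents: N = 50, allocated 1:1, so 25 per arm; sex as the only stratum; entry at about the top 20-25% of loneliness scores. Assumed, because the documents do not give them: two-sided 5% level, no dropout, the pre-post correlation r, the SDs, and an illustrative effect of 0.5 SD. There is no power calculation in the plan to reproduce.

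**Step 1: what the planned test is.** With two time points and complete data, the interaction F equals the squared t on change scores. A numerical check gave F = t² = 0.2205.

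**Step 2: variances per person.** With pre SD s0, post SD s1 and slope b = r·s1/s0:

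- change score: s0² + s1² − 2·r·s0·s1
- ANCOVA: s1²(1 − r²)
- difference: s0²(1 − b)², which is zero only at b = 1

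With equal SDs the ratio ANCOVA/change is (1 − r²)/(2(1 − r)) = (1 + r)/2. Estimating the slope multiplies the ANCOVA variance by about 1 + 1/46 = 1.022. At r = 0.5 this gives 0.75 × 1.022 = 0.77.

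**Step 3: size without selection, equal SDs.** Noncentral t with 48 df (change) and 46 df (ANCOVA with baseline and sex). The last column is 50 divided by the net ratio: the number the change-score test needs to match ANCOVA in 50.

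| r | Net variance ratio | Detectable effect at 80% power, change → ANCOVA (SD) | Power for 0.5 SD | Matching N |
|---|---|---|---|---|
| 0.3 | 0.66 | 0.96 → 0.78 | 31% → 43% | 75 |
| 0.5 | 0.77 | 0.81 → 0.71 | 41% → 51% | 65 |
| 0.7 | 0.87 | 0.63 → 0.58 | 61% → 67% | 58 |
| 0.8 | 0.92 | 0.51 → 0.49 | 78% → 81% | 54 |
| 0.9 | 0.97 | 0.36 → 0.36 | 97.2% → 97.5% | 52 |

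With unequal SDs the slope governs, not r. At r = 0.8 and s1/s0 = 1.25, b = 1 and the ratio before slope cost is 1.00. At r = 0.5 and s1/s0 = 0.8, b = 0.4 and the ratio is 0.57.

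**Step 4: allowing for the entry cut-off.** A normal screening score S truncated to its top 20-25% keeps a variance of 0.219-0.242. Write k for 1 minus that variance. Among those selected, with baseline B and post score P:

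- Var(B) = 1 − k·ρ(SB)²
- Var(P) = 1 − k·ρ(SP)²
- Cov(B,P) = ρ(BP) − k·ρ(SB)·ρ(SP)
- ratio = [Var(P) − Cov²/Var(B)] / [Var(B) + Var(P) − 2Cov]

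Example: ρ(SB) = ρ(BP) = 0.5, ρ(SP) = 0.25, top 25% (k = 0.758). Then Var(B) = 0.8105, Var(P) = 0.9526 and Cov = 0.4053. The ratio is 0.750/0.953 = 0.787, or 0.80 net.

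Net ratios by unselected baseline-post correlation:

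| Structure | 0.3 | 0.5 | 0.7 | 0.8 | 0.9 |
|---|---|---|---|---|---|
| All three correlations equal | 0.64 | 0.70-0.71 | 0.77-0.78 | 0.82 | 0.88-0.89 |
| Screening-post is the product of two equal adjacent correlations | 0.68 | 0.80-0.81 | 0.92 | 0.97 | 1.00 |
| Screening-baseline 0.95 | 0.87-0.88 | 0.92-0.93 | 0.97 | 0.99 | 1.01 |
| Screening score reused as the pre value | 0.90-0.91 | 0.95 | 0.98 | 1.00 | 1.01 |

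**Step 5: if baseline depressive symptoms are in both models.** Let depression correlate a with baseline loneliness, and with the post score only through it (correlation a·r). The change-score variance becomes 2(1 − r) − a²(1 − r)², and the ANCOVA variance stays at 1 − r². For a = 0.3-0.7 the ratio before slope cost is 0.77-0.85 at r = 0.5 (at a = 0.7: 0.75/0.8775 = 0.85) and 0.86-0.92 at r = 0.7. If depression correlates 0.5 with both scores, the ratio at r = 0.5 is 0.67. Depression does not stand in for baseline loneliness.

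**Step 6: validity and worst case.** In simulation (N = 50, blocks of 4 within sex, r = 0.5, no selection) the change score and ANCOVA rejected a true null in 4.9% and 5.1% of trials. Power for 0.5 SD was 40.8% and 50.7%, and mean estimates were 0.49-0.50 for both. If the slope is exactly 1, ANCOVA has about 2% more variance and a detectable effect about 1% larger.

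**The case against.** Time by condition is a standard, valid analysis that answers the stated question about change, so nothing is broken. The gain cannot be fixed from the documents. The largest figures come from an unselected, equal-variance sample, whereas everyone here is selected on loneliness. At correlations of 0.7 or more, three of the four selection structures give a net cut of 8% or less, and at 0.9 those three give none. The term repeated measures also names no estimator, so a baseline-constrained model is not ruled out.

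Much of this stands. The point is about efficiency, and the gain may be small or absent. It does not defeat the recommendation, which does not depend on knowing r: the loss is bounded at about 2% in variance, and the gain at low to moderate correlations is many times that. No constraint is written, so as it stands the interaction is the change-score test.

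Two practical cautions also stand. The document carries dates of January 2022 and December 2024 and does not give the trial's status; a switch made after unblinded outcomes are known would not carry the weight of a pre-specified analysis. And participants may be removed for side effects, so post scores may be missing. ANCOVA and the constrained mixed model agree with complete data but treat incomplete participants differently, so one must be named as primary.

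**Conclusion.** The point holds as an efficiency improvement. The planned test is valid, and no conclusion drawn from it would be wrong for this reason. On the assumptions above, adjusting for baseline loneliness reduces the variance by 3-34% without selection (r = 0.9 down to 0.3). With selection and a separately measured baseline, the net reduction is about 1-36% for correlations of 0.3-0.8; at 0.9 the result lies between a 12% cut and a 1% loss. If the screening score were reused as the pre value, the net cut would be 9-10% at 0.3, about 5% at 0.5 and nil at 0.8. The algebra is exact for complete data; the sizes depend on correlations and SDs that the documents do not give. The change should be made because the downside is small and the baseline score is already collected.

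**What to change.** State the primary loneliness analysis as an ANCOVA of post-intervention loneliness on condition, baseline-session loneliness and sex. Alternatively, state a mixed model with baseline means constrained equal across arms, which keeps the SAP's repeated-measures framework. Name one of them as primary. Say that the baseline is the session score, not the telephone screening score.

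Use the same form for the other pre/post outcomes. For reaction time, take the close-other minus control difference as the outcome and its own baseline value as the covariate. Sex adds little power; it is included to match the stratified randomisation.

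If depressive symptoms are to be controlled, state when they are measured. Use the baseline score in any model meant to estimate the total effect of naproxen, because the Study Protocol itself says that "naproxen can reduce depressive symptoms in both animals and humans"; adjusting for a post-treatment score could remove part of the effect.

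The cost is SAP wording and two degrees of freedom (48 to 46), with no new data. Fix the change before unblinded outcomes are seen; if that point has passed, report the adjusted model as a sensitivity analysis.
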